1 PROTOCOL SUMMARY

1.1 SYNOPSIS

Title:	Early vs. Interval Postpartum IUD Insertion: A Multi-Site Randomized Controlled Non-Inferiority Trial
Study Description:	This is a randomized controlled non-inferiority trial comparing the expulsion rate of early postpartum IUDs (intrauterine devices) inserted between 2-4 weeks postpartum to the standard interval placement at 6-8 weeks postpartum
Objectives:	Primary Objective: Complete IUD expulsion at 6 months postpartum Secondary Objectives: Partial IUD expulsion at 6 months postpartum, IUD utilization, IUD removal, IUD perforation, pelvic infection, pain, vaginal bleeding, and user satisfaction at 6 months postpartum
Endpoints:	Primary Endpoint: Speculum and ultrasound evaluation Secondary Endpoints: Speculum, ultrasound and x-ray evaluation, self-reported outcomes (survey results)
Study Population:	Postpartum women who delivered an infant within the previous 10 days
Phase:	N/A
Description of Sites/Facilities Enrolling Participants:	Academic medical centers: the University of California, San Diego (UCSD); University of New Mexico (UNM); University of Illinois, Chicago (UIC); and Naval Medical Center, San Diego (NMCS)
Description of Study Intervention:	Postpartum insertion of IUDs at 2-4 weeks after delivery vs. 6-8 weeks after delivery
Study Duration:	2 years
Participant Duration:	6 months (with optional 12-month participation offered)

2 INTRODUCTION

2.1 STUDY RATIONALE

Intrauterine devices (IUDs) provide highly effective contraception and are historically placed at the interval six-week PP visit for women who desire intrauterine contraception. Since ovulation can occur as early as 25 days postpartum, there is a risk that women could become pregnant between 4-6 weeks postpartum.

The early postpartum (EPP) period, 2-4 weeks postpartum, could be a convenient time for women to receive contraception, including IUDs. Women can't become pregnant in the first 25 days postpartum. The visit can be co-located with other health care visits, such as well baby visits, that occur in this time frame.

Offering women EPP IUDs may decrease the risk of undesired pregnancy and rapid repeat pregnancy.

2.2 BACKGROUND

Intrauterine devices (IUDs) provide highly effective contraception and are historically placed at the interval six-week postpartum visit for women who desire intrauterine contraception. Since ovulation can occur 25 days postpartum, there is a risk that women could become pregnant between 4-6 weeks postpartum.

Immediate postpartum (IPP) IUD placement, within 10 minutes of delivery, is safe and effective as well as convenient for providers and patients (ACOG, 2016). Despite the benefits of IPP IUD insertion, there are significant barriers to widespread implementation, most importantly a lack of reimbursement mechanisms and training. Although efforts are currently in place to increase access to IPP IUDs, they are developing slowly, and additional strategies are urgently needed to allow for flexibility and multiple options for provision of highly effective contraception in the postpartum period.

Both immediate and interval IUD insertion carry unique risks. IPP IUD insertion is associated with an increased risk of expulsion (IUD being pushed out of the uterus) with rates as high as 24-38% (Chen, 2011; Goldwaite, 2017) compared to IUDs placed at 6 weeks PP 3-5% (Chen, 2011). However, interval IUD insertion at 6 weeks postpartum is associated with a small increase in the risk of uterine perforation (IUD going through the uterine wall), particularly among breastfeeding women (Heinemann, 2015) and there is a risk that women will become pregnant by 6 weeks postpartum leading to undesired pregnancies and rapid repeat pregnancies.

The early postpartum (EPP) period, 2-4 weeks postpartum, could be a convenient time for women to receive contraception, including IUDs. Women can't become pregnant in the first 25 days postpartum. The visit can be co-located with other health care visits, such as well baby visits, that occur in this time frame.

Three studies have shown that EPP IUD placement is feasible and acceptable (Baldwin 2016, Zerden 2017, Chen 2017). There were no perforations among participants in these studies and no complete expulsions. Partial IUD expulsion rates were low (2-5% at 6 months). However, these studies were not powered to determine IUD expulsion. The purpose of this study is to compare the expulsion rate of EPP IUDs inserted between 2-4 weeks postpartum to the standard placement timing at 6-8 weeks postpartum. This trial will provide a key piece of missing data that will allow women to be counseled appropriately about the benefits and risks of EPP IUD insertion and potentially allow women access to all methods of contraception, including the most effective methods of contraception, at time points earlier than the traditional six-week postpartum visit.

2.3 RISK/BENEFIT ASSESSMENT

2.3.1 KNOWN POTENTIAL RISKS

1. Loss of confidentiality: there is risk of stress, emotional distress, inconvenience, and possible loss of privacy associated with participating in a research study. There will be a need for medical record access to assess patient demographics and clinical outcomes. Most study data will be stored in the HIPAA-secure online REDCap database. Any printed study data (such as consent forms) will be secured in a locked cabinet/filebox, and only those directly involved in the study will have access to these including the investigators who will process the data. Data will only be saved under a secure file on a computer requiring a log-in password. Data will be shared between institutions and UCSD using REDCap, which is a secured HIPAA-compliant web application (<https://redcap.ucsd.edu>). NMCSD is not able to enter data directly into REDCap. NMCSD will, instead, use paper copies of all study instruments and share them via secure fax to UCSD; UCSD staff will enter data into REDCap. Once data is entered into REDCap, UCSD will shred the paper copies. Shared patient identifiers include: patient initials, date of service, baby delivery date. Consent will be obtained in the patient's private postpartum room, in the private clinical space where participant can ask questions without feelings of embarrassment or discomfort, and/or over the phone from a private office. The physical exam will be conducted in a private examination room.
2. IUD expulsion or uterine perforation risk: there is a risk that IUD expulsion and uterine perforation could be greater than in the study group (EPP) compared to the standard of care group. Currently available data suggest that the risk of expulsion and perforation will be less than or equal to the risk of expulsion and perforation associated with the standard of care. There have been over 200 women who have had documented EPP IUDs placed and the risks of expulsion have been low (<4%) and there have been no documented perforations (Baldwin 2016, Zerden 2017, Chen 2017). In addition, ultrasound studies have shown that approximately two-thirds of uterine involution occurs by 14 days PP which could be protective against expulsion (Belachew, 2012) In the EPP period the uterine wall is thicker than 6 weeks postpartum, which could be protective against perforation (Watanagara, 2015). The practice of inserting IUDs at this time is approved and considered to be a category 2 practice (benefits outweigh the risks) from the CDC Medical Eligibility Criteria (CDC, Medical Eligibility Criteria, 2016). However, the data on this practice are minimal and thus there are potential risks to IUD insertion at this time which is why this study is urgently needed. All patients will be informed of possible IUD expulsion and uterine perforation (known and unknown). Clinicians may also use ultrasound guidance for placement if they feel that ultrasound will mitigate the risk of expulsion or perforation. Participants will be assessed at a follow-up visit for IUD expulsion and uterine perforation. A study clinician will conduct a bimanual pelvic exam and a transvaginal ultrasound at this visit and provide any care clinically required to address any IUD side effects or complications.
3. There is a risk that an IUD could be placed when a woman is already pregnant. This is true only during the standard of care and it is a potential benefit of the EPP that women cannot yet be pregnant so soon after delivery (ovulation can't occur until at least 25 days postpartum). Any woman who is > 25 days postpartum who has an IUD placed will be assessed for the risk of new pregnancy (will be asked if she has had unprotected intercourse and will be assessed for lactational amenorrhea). If > 25 days postpartum and at risk for pregnancy, then a urine pregnancy test will be done prior to IUD placement and an IUD will not be placed if a urine pregnancy test is positive until new pregnancy has been excluded. A clinician will see the patient and evaluate whether the positive

pregnancy test represents a new pregnancy or residual positive pregnancy test from the recently delivered pregnancy.

2.3.2 KNOWN POTENTIAL BENEFITS

Patients may not experience a direct benefit from participation in this study. However, this study will help determine if IUDs can be provided during the early postpartum period with low expulsion rates and high patient satisfaction rates. There may be a benefit to women in the EPP group to avoid unplanned early repeat pregnancies.

2.3.3 ASSESSMENT OF POTENTIAL RISKS AND BENEFITS

The potential benefit of early postpartum contraception (the potential for decreased unwanted pregnancies, possible decrease in expulsion, and possible decrease in perforation) outweighs the potential risks of increase in expulsion and/or uterine perforation.

3 OBJECTIVES AND ENDPOINTS

OBJECTIVES	ENDPOINTS	JUSTIFICATION FOR ENDPOINTS
Primary		
To determine if the risk of complete expulsion of EPP IUDs is non-inferior to interval PP IUDs	Diagnosis of IUD expulsion by speculum and ultrasound exam at 6 months postpartum. Expulsion defined as no IUD within the uterus by ultrasound or x-ray.	We propose that greater than or equal to a 6% difference in expulsion at 6 months postpartum between the two arms is clinically meaningful (6% non-inferiority margin).
Secondary		
To assess the proportion of participants utilizing the IUD at 6 months	Transvaginal and speculum exam to confirm presence of the IUD at 6 months.	From a public health perspective, the duration of IUD use is important for pregnancy prevention.
To determine if the risk of partial expulsion of EPP IUDs is non-inferior to interval PP IUDs	Diagnosis of IUD expulsion by speculum and ultrasound exam at 6 months postpartum. Partial expulsion defined as IUD protruding from the external cervical os on speculum exam or any part of the IUD seen below the internal cervical os on transvaginal ultrasound.	We propose that greater than or equal to a 6% difference in partial expulsion and perforation at 6 months postpartum between the two arms is clinically meaningful (6% non-inferiority margin).
Tertiary/Exploratory		
To assess the risk of perforation after EPP IUD compared to interval postpartum IUDs	IUD not visible in uterus on transvaginal ultrasound, but visible on pelvic x-ray at 6 months.	

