All women will be scheduled to have a routine postpartum visit with their designated prenatal care provider **between 42-56 days postpartum** according to the standard of care at the health centers. Women will be scheduled to see a nurse midwife or physician based on their obstetrical history and prenatal care. Women in the interval group will be assessed for IUD placement at this visit per the standard of care at the center. IUDs will be placed by the patient's usual prenatal provider or any provider that the patient would normally be referred to for IUD placement. Whether ultrasound guidance is used for placement will be at the discretion of the clinician. Participants will be compensated with a \$20 gift card for their time and participation. Participants will be asked to complete either the insertion visit questionnaire or the string check questionnaire depending on their assignment group. Providers will be compensated with a \$5 gift card for their time completing a brief questionnaire for every patient seen at six weeks postpartum.

D. Optional String Check Visit:

Whether a follow-up string check visit is scheduled after six weeks will be at the discretion of the clinician according to standard practice of the clinic. String checks are not recommended by the CDC but are common practice. If a string check is scheduled by the clinician at any time (according to their personal practice or participant needs) then the participant will be asked to complete the string check questionnaire at that time.

e. Six Month Follow Up Visit

All women will be scheduled for a 6-month follow up study visit to assess for IUD expulsion, perforation, pregnancy, IUD removals and acceptability. A study clinician will conduct a bimanual pelvic exam, a speculum exam, and a transvaginal ultrasound at this visit. Women will also be asked to complete the 6-month study questionnaire and will be compensated with a \$20 gift card for their time and participation. The clinician will attempt to stay blinded to the participant's group assignment by not reviewing the medical chart prior to the visit.

f. 12 Month Optional Follow Up Call

During baseline survey data collection, all women will be asked if they consent to a 12-month follow up phone call to assess for IUD expulsion, perforation, pregnancy, IUD removals and acceptability.

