9.3 POPULATIONS FOR ANALYSES

The following datasets will be utilized for analysis:

- Intention-to-Treat Analysis Dataset: All participants randomized with known outcomes at the 6 month follow up visit*.
- Modified Intention-to-Treat Analysis Dataset: Participants who received an IUD within 6 months of delivery with known outcomes at the 6 month follow up visit*.
- Per-Protocol Analysis Dataset: Participants who received an IUD within the specified timeframe as designated by their group assignment with known outcomes at the 6 month follow up visit (14-28 days in the early group and 42-56 days in the interval group)*.

*participants known to have an IUD outcome by ultrasonography, pelvic examination, or a contact up to 240 days postpartum will be included.

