9.4 STATISTICAL ANALYSES

9.4.1 GENERAL APPROACH

9.4.2 ANALYSIS OF THE PRIMARY EFFICACY ENDPOINT(S)

Our primary outcome, the proportion of women with complete IUD expulsion at 6 months after delivery in the two groups, will be compared in the modified intention-to-treat (MITT) cohort using the Wald test. Women who change their mind about receiving the IUD after randomization, choose to receive the IUD after 6 months, or women who choose not to participate in the study any time after randomization, will be excluded from analysis for the MITT analysis. In addition, we will present a per-protocol analysis. The per-protocol analysis will include women who received their treatment according to the timeframe in which they were randomized. For the early IUD insertion group, per-protocol analysis will include women with documented receipt of the IUD insertion between 14 and 28 days postpartum. For the interval IUD insertion group, the per-protocol analysis will include only women with documented receipt of a postpartum IUD between 42-56 days postpartum. In both the MITT and per-protocol analyses IUD expulsion rates will be compared using the 2-sided test of noninferiority. If the CI for the risk difference does not cross the prespecified 6% margin, noninferiority will be confirmed.

We will consider imputing missing data. However, if one group had no or few expulsion outcomes the model may not converge.

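### The primary endpoint is defined by whether an IUD is in the uterus at 6 months, so read literally it misses expelled-and-replaced IUDs and takes in removals and possibly perforations

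*Combined protocol and SAP*

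**What the plan says.** The primary row of the table in section 3 (Objectives and Endpoints) gives the method and date, "Diagnosis of IUD expulsion by speculum and ultrasound exam at 6 months postpartum", and then the definition: "Expulsion defined as no IUD within the uterus by ultrasound or x-ray". The exploratory row of the same table defines perforation as "IUD not visible in uterus on transvaginal ultrasound, but visible on pelvic x-ray at 6 months".

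Other sections treat these as different outcomes:

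- The synopsis (1.1) lists as secondary objectives "Partial IUD expulsion at 6 months postpartum, IUD utilization, IUD removal, IUD perforation".
- Section 8.1e says the 6-month visit is to "assess for IUD expulsion, perforation, pregnancy, IUD removals and acceptability".
- Section 2.2 explains expulsion in passing as the device being forced out of the uterus, and perforation as the device passing through its wall.

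The analysis sections add no classification rule. Section 9.4.2 names the primary variable as "the proportion of women with complete IUD expulsion at 6 months after delivery in the two groups". The primary analysis set in section 9.3 is "Participants who received an IUD within 6 months of delivery with known outcomes at the 6 month follow up visit", with a footnote that also admits outcomes learned by examination, ultrasound or contact up to 240 days. Replacement of an expelled IUD is not mentioned anywhere.

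On examinations, section 8.1e says "A study clinician will conduct a bimanual pelvic exam, a speculum exam, and a transvaginal ultrasound at this visit". X-ray is not in that list. The synopsis names x-ray for secondary endpoints only, while section 3 uses it in the primary definition as well.

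**The concern.** The definition asks whether an IUD is in the uterus on one date. The question of interest is whether the inserted IUD was lost spontaneously at any time since insertion. The two differ for three kinds of participant:

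- **Expelled, then replaced.** An IUD is in the uterus at 6 months, so the expulsion is not counted. This shrinks any true difference between arms and favours a non-inferiority claim.
- **Deliberately removed.** No IUD is in the uterus, so the literal wording counts an expulsion. Equal removal rates raise the apparent rate in both arms and cost power. Unequal rates bias the comparison.
- **Perforated.** An IUD not seen in the uterus on ultrasound but seen on pelvic x-ray meets the perforation definition and can also meet the expulsion definition.

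Equal misclassification in the two arms cannot be taken for granted. The visit is fixed in time since delivery, while insertion is at 14-28 or 42-56 days, so early IUDs have about 28 more days (42 − 14, or 56 − 28) in which to be removed, or expelled and replaced. At the planned 4% rate only about 6.5 events per arm are expected (163 × 0.04), so reclassifying a few women can change the result. The trial is also unblinded, so the classification rules should be fixed before the data are seen.

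**Working it through.** **Inputs from section 9.2:** 4% expulsion in the interval arm, 6-point margin, 80% power, 202 per arm, 15% loss to follow-up, 5% of IUDs not placed. Section 9.2 states both a two-sided 0.05 level and a one-sided 0.25% level. I use one-sided 0.025, the only one of the levels tried (one-sided 0.05, 0.025 and 0.0025) that reproduces the stated total.

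**Reproducing the plan's figure.** n = (1.960 + 0.842)² × 2 × 0.04 × 0.96 / 0.06² = 167.4, so 168 per arm. Then 168 × 1.20 = 201.6, so 202 per arm and 404 in total, as stated.

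**Evaluable number.** 202 × 0.85 × 0.95 = 163 per arm.

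**Assumed, because the documents give no figures:** 10%, 20% or 30% of expelled IUDs replaced before the visit, the same share in both arms; removal by 6 months of 5% or 10%, equal in both arms.

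**Replaced expulsions missed.** Take true rates at the margin, 10% early v 4% interval, where a false non-inferiority finding should occur 2.5% of the time. If a share f is missed, the observed rates are 0.10(1 − f) and 0.04(1 − f), the observed difference is 0.06(1 − f), and

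P(declare non-inferior) = Φ[(0.06 − observed difference)/SE − 1.96], with SE = √{[p₁(1 − p₁) + p₂(1 − p₂)]/163}.

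| f | Observed rates | Difference | SE | P(declare non-inferior) |
|---|---|---|---|---|
| 0 | 10.0% v 4.0% | 6.0 points | 0.0281 | 2.5% |
| 0.1 | 9.0% v 3.6% | 5.4 points | 0.0267 | 4.1% |
| 0.2 | 8.0% v 3.2% | 4.8 points | 0.0253 | 6.9% |
| 0.3 | 7.0% v 2.8% | 4.2 points | 0.0238 | 11.4% |

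**Removals counted as expulsions.** With true expulsion of 4% in both arms, power = Φ[0.06/√(2p(1 − p)/163) − 1.96], where p is the apparent rate.

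| Removals counted | p | Power |
|---|---|---|
| none | 4% | 79% |
| 5% | 9% | 47% |
| 10% | 14% | 34% |

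If removals apply only to women who have not expelled, p is 0.04 + 0.96 × 0.05 = 8.8% or 0.04 + 0.96 × 0.10 = 13.6%, and power is 48% or 35%.

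**Perforation.** There is no rate to work with. Whether the definitions overlap depends on how the two imaging methods in the primary definition combine. If the IUD must be unseen on both, a perforated IUD visible on x-ray is excluded. If it need only be absent from the uterus on either, that IUD meets both definitions.

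**The case against.** The strongest reply is that the intent is plain. Section 2.2 describes expulsion as the device being forced out, which a clinician's removal is not. Removal is listed as its own outcome in section 1.1, asked about separately at the 6-month visit, and given its own treatment in section 9.4.3. A sensible analyst would not code a recorded removal as an expulsion. This stands. A reader might infer that the reported rate will be inflated by removals; the documents do not support that, and the fall in power to 47% or 34% describes literal application only. Nor would equal removals produce false non-inferiority, since they only reduce power.

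On perforation, x-ray has an evident purpose in the primary definition: to show that a device unseen on ultrasound is absent and not displaced. Section 2.3.1 reports no perforations in over 200 early placements. It would be too strong to say that perforations are certainly double-counted.

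On replacement, ascertainment is not confined to one scan: there is a 6-month questionnaire, and the section 9.3 footnote accepts other contacts. This helps detect an earlier expulsion, but it does not make that expulsion count, because the definition still asks about the uterus at 6 months. This part of the objection does not stand.

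On x-ray, a reader might infer that the trial does not use it at all. Sections 1.1 and 3 both name it, and section 8.1e may list only what every woman receives. What remains is that the three sections do not agree on its place in the 6-month assessment.

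**Conclusion.** The concern holds as a defect in the definition that should be fixed, not as proof that the primary rate will be wrong. Section 3 states a rule that, applied literally, gives a different count from the one that sections 1.1, 2.2 and 8.1 imply, and sections 9.3 and 9.4.2 do not repair it.

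Replaced expulsions are the most important part: nothing in the plan addresses them, and the error runs toward declaring non-inferiority. At the margin, false non-inferiority rises from 2.5% to 4.1%, 6.9% or 11.4% if 10%, 20% or 30% of expulsions are missed. Miscounted removals would cost much power but are less likely in practice. The perforation overlap depends on the reading and cannot be sized.

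The results rest on 163 evaluable women per arm, one-sided 0.025 and the normal approximation. The removal and replacement rates are assumptions, so the figures show sensitivity and are not forecasts.

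**What to change.** In sections 3 and 9.4.2:

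- Define complete expulsion as spontaneous loss of the study IUD from the uterus at any time from insertion to the 6-month assessment, established by examination, imaging or a documented report.
- Count an IUD that was expelled and then replaced as an expulsion.
- Classify deliberate removal of an IUD not already expelled as removal, not expulsion.
- Classify an IUD that has left the uterus through its wall as perforation. Do not count as perforation an IUD lying in the cervix or vagina; a rule based only on being outside the uterus would turn such a case into a perforation.

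Reconcile sections 1.1, 3 and 8.1e on whether x-ray is part of the 6-month assessment, since both definitions in section 3 rely on it and 8.1e does not list it.

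The cost is about one paragraph across sections 3 and 9.4.2 and one line in 8.1e. Removals, perforations and x-ray are already in the plan, so no new outcome is added and the sample size calculation is unchanged.

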8.2 SAFETY AND OTHER ASSESSMENTS

We will convene a Data Safety and Monitoring Board (DSMB) to review adverse events if any of the following occur:

- At the midpoint of enrollment
- If there is 1/3rd the expected enrollment at 6 months
- More than four serious adverse events at any time deemed definitely, probably, or potentially related to the intervention
- Rate of any serious adverse events is greater than 1% (including blood transfusion, hospitalization related to IUD, surgery related to IUD, death, IUD perforation, venous thromboembolism)

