9.4.3 ANALYSIS OF THE SECONDARY ENDPOINT(S)

Partial IUD expulsion and perforation will be analyzed with the same methods as the primary outcome. IUD discontinuation over the six-month study period will also be analyzed using survival analysis. Data will be censored either (1) at the last date of contact if a participant is lost to follow up or (2) time of IUD removal. The Log-rank test will be used for an unadjusted comparison of the two survival functions. This will be presented graphically using Kaplan-Meier curves.

For other secondary outcomes, normally distributed, continuous variables will be compared using Student's t-tests as appropriate. The Mann-Whitney U test will be used to compare other continuous variables that are not normally distributed. Proportions will be compared using chi-square tests. For small cell sizes, Fisher's exact test will be used as appropriate.

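### The perforation endpoint is a status at 6 months, so a perforation found and treated earlier does not meet it and could be counted as a complete expulsion

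*Combined protocol and SAP*

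**What the plan says.** The objective in section 3 is "To assess the risk of perforation after EPP IUD compared to interval postpartum IUDs", listed as tertiary/exploratory. The endpoint beside it is "IUD not visible in uterus on transvaginal ultrasound, but visible on pelvic x-ray at 6 months". The documents contain no other definition of perforation.

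The same table defines the primary outcome thus: "Expulsion defined as no IUD within the uterus by ultrasound or x-ray".

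Section 9.4.3, which covers secondary endpoints, states: "Partial IUD expulsion and perforation will be analyzed with the same methods as the primary outcome". Under section 9.4.2 those methods are a comparison of proportions with a Wald test and a confidence interval for the risk difference.

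On ascertainment, section 8.1 states: "All women will be scheduled for a 6-month follow up study visit to assess for IUD expulsion, perforation, pregnancy, IUD removals and acceptability". The procedures follow: "A study clinician will conduct a bimanual pelvic exam, a speculum exam, and a transvaginal ultrasound at this visit". No x-ray is in that list. The footnote to the analysis sets in section 9.3 reads: "participants known to have an IUD outcome by ultrasonography, pelvic examination, or a contact up to 240 days postpartum will be included".

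Perforation also has a safety route. In section 8.2 the examples of serious adverse events include "surgery related to IUD, death, IUD perforation, venous thromboembolism". Section 8.3.4 requires every adverse event during the study to be documented, and section 9.4.4 puts serious treatment-emergent events in a table.

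**The concern.** The objective is a cumulative risk: did placement lead to a perforation at any time in follow-up? The endpoint is a state on one date: is an IUD outside the uterus at 6 months? The two agree only for perforations still unrecognised or untreated at that date. A perforation noticed at insertion or at an intervening visit, and dealt with, is the kind of event the objective is about, yet it falls outside the stated rule.

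Two results are at stake. The perforation comparison could lose part or all of its few events, and could then disagree with the serious adverse event table with no rule for which count governs. In addition, some of these women could enter the primary outcome, because the expulsion definition does not separate an IUD that was expelled from one that perforated and was taken out.

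Perforation matters to the trial's argument. Section 2.3.1 names it as a risk of early placement, and section 2.3.3 cites a possible decrease in perforation among the benefits.

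**Working it through.** **1. Apply the definitions literally to each type of case.**

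| Case | Perforation endpoint (section 3) | Complete expulsion (section 3) |
|---|---|---|
| Perforated IUD still outside the uterus at 6 months, x-ray taken | Met | Wording also met: no IUD in the uterus |
| Found earlier, IUD removed, not replaced | Not met: nothing on x-ray | Wording met: no IUD in the uterus |
| Found earlier, IUD removed and replaced | Not met: new IUD seen in the uterus | Not met |

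The two earlier-found cases fail the perforation endpoint. The first two rows show that perforation and complete expulsion are not mutually exclusive as written.

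**2. Look for text that widens the rule.** Section 9.4.3 names the analysis and leaves the definition unchanged. The section 9.3 footnote settles who enters the analysis sets, not what counts as a perforation. Section 8.1 has the 6-month visit assess perforation and removals, but does not say that a past perforation meets the endpoint. Sections 8.2, 8.3.4 and 9.4.4 lead to a safety table, and nothing links that table to the comparison.

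**3. Number of evaluable women.** The plan gives no figure for perforation. Its sample size is for expulsion and serves here only as the base for counts. With 4% in both arms, a 6% margin, one-sided 2.5% and 80% power:

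n = (1.960 + 0.842)² × 2 × 0.04 × 0.96 / 0.06² = 168 per arm after rounding up; 168 × 1.20 = 201.6, so 202 per arm and 404 in total, as section 9.2 states.

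After the plan's 15% loss and 5% non-placement, 202 × 0.80 = 161.6. I use 161 per arm, 322 in total.

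**4. Expected perforations.** The documents give no rate. Section 2.3.1 reports none in over 200 early placements. The one-sided 95% upper bound for 0 of 200 is 1 − 0.05^(1/200) = 1.5%. I assume a range of 0.1% to 1.5%, equal in both arms. Expected cases per arm are 161 × p. The chance of at least one counted case in the trial is 1 − (1 − q)^322, where q is p times the share not treated before 6 months.

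| Assumed rate p | True cases per arm | Counted per arm if half are treated early | Chance of ≥1 case, all counted | Chance of ≥1 case, half treated early |
|---|---|---|---|---|
| 0.1% | 0.16 | 0.08 | 27.5% | 14.9% |
| 0.5% | 0.81 | 0.40 | 80.1% | 55.3% |
| 1.0% | 1.61 | 0.81 | 96.1% | 80.1% |
| 1.5% | 2.42 | 1.21 | 99.2% | 91.1% |

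If all are treated before 6 months, the literal endpoint counts none at any rate. The one-half share is an illustration, not a figure from the documents.

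**5. Effect on the primary outcome.** Each perforation counted as a complete expulsion moves that arm's proportion by 1/161 = 0.62 percentage points, and two by 1.24. The margin is 6 points, and the plan's 4% rate implies 161 × 0.04 = 6.4 expulsions per arm.

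**The case against.** The strongest reply is that the plan expects history to be used. The 6-month visit is meant to cover perforation and removals and includes a questionnaire. The optional 12-month telephone call also asks about perforation, which cannot depend on an x-ray that day. Outcomes known from a contact up to 240 days postpartum are accepted. Taken literally, the expulsion wording would sweep in elective removals too, so investigators must already be using judgement. This shows that the information will often be available. It does not show that the perforation endpoint will use it, because no sentence says so.

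A reader might infer that every perforation treated early is scored as no perforation. The documents do not say that. They give no scoring rule for these women, who could be non-events, unclassified or complete expulsions.

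A reader might also infer that the trial would report no perforations at all. That does not follow either. Section 8.2 lists perforation among serious adverse events, and section 9.4.4 tabulates them, so a treated case should be visible there. The phrase in section 8.2 about events at any time belongs to a different bullet from the one naming perforation, but section 8.3.4 still requires events during the study to be documented.

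Finally, a reader might infer a bias in favour of early placement, since early-arm women attend the 42–56 day visit with the IUD in place while interval-arm women attend for insertion. Unequal omission is possible but not shown. Section 8.1 lists no imaging at that visit, later string checks are discretionary in both arms, and perforations seen at insertion would be omitted in either arm.

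It also stands that section 3 ranks perforation as exploratory, although the synopsis and section 9.4.3 treat it as secondary. With so few events the comparison will be largely descriptive under any definition.

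**Conclusion.** The point holds as a mismatch between objective and endpoint. Followed as written, the rule leaves perforations found and treated before 6 months out of the perforation comparison. They would appear only in the serious adverse event table, and those whose IUD was not replaced could be miscounted as complete expulsions.

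On the assumed rates, one or two omissions are most or all of an arm's expected count. The possible effect on the primary outcome is smaller, at 0.62 percentage points per case. These sizes rest on the assumed range of rates, equal rates in the two arms and about 161 evaluable women per arm. The mismatch itself rests on the wording alone. The direction of any resulting bias between arms is not established.

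**What to change.** In section 3, define perforation as any perforation documented from insertion through the 6-month assessment, whether by imaging, at surgery or in the records, and whether or not the IUD has since been removed or replaced. Add three statements:

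- Before analysis, the perforation endpoint is reconciled with the serious adverse event reports, so that the two counts agree or any difference is explained.
- A perforation is not counted as a complete expulsion.
- Perforation has one rank, secondary or exploratory, used alike in the synopsis, section 3 and section 9.4.3.

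The x-ray in the section 3 definition and the list of 6-month procedures in section 8.1 should also be reconciled.

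The cost is a few sentences and a cross-check of serious adverse event records. The events are already to be captured under sections 8.2 and 8.3.4, so the new definition needs no extra visit and no change in sample size.
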